**Hypotheses and Analytic Plan**

**NCT# NCT05789238**

**Version Date: 05/18/2023**

## **Hypotheses**

The overall purpose of this study is to assess the impact of different nutrient profiles for magnifying glass front-of-package labels on consumer choices in an online grocery store.

### *Primary Outcomes*

The primary outcomes are the total sugar (g), saturated fat (g), and sodium (mg) of products purchases.

We hypothesize that:

1. Compared to the no-label control, the ANVISA magnifying glass and PAHO magnifying glass will lead to reduced total sugar of products purchased.
2. Compared to the no-label control, the ANVISA magnifying glass and PAHO magnifying glass will lead to reduced total saturated fat of products purchased.
3. Compared to the no-label control, the ANVISA magnifying glass and PAHO magnifying glass will lead to reduced total sodium of products purchased.

### *Secondary Outcomes*

The secondary outcomes are the percentage of ultra-processed products purchased (as defined by the NOVA classification), perceived healthfulness of unhealthy products, perceived product appeal of unhealthy products, concern about health effects of unhealthy products, ability to identify high sugar/saturated fat/sodium content of unhealthy products (as per the PAHO nutrient profile model, which is stricter than ANVISA's), and noticing of the product label.

We hypothesize that, compared to the no-label control, the ANVISA magnifying glass condition and PAHO magnifying glass condition will lead to:

1. Lower percentage of ultra-processed products (as defined by the NOVA classification) purchased.
2. Lower perceived healthfulness of unhealthy products.
3. Lower perceived product appeal of unhealthy products.
4. Higher concern about health effects of unhealthy products.
5. Higher ability to identify high sugar/saturated fat/sodium content of unhealthy products.
6. Higher noticing of the front-of-package label.

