## **STATISTICAL CONSIDERATION**

### **Statistical Methods**

The study is a randomized controlled trial. The analysis will rely on random assignment to identify the effect of each type of front-of-package label nutrient profile model on consumer choices.

We will conduct a soft launch with 100 participants to check randomization and data quality. If randomization is working properly and there are not apparent issues with the data collection, we will resume data collection until the final sample is achieved. The original participants from the soft launch will be included in the final dataset. If randomization is not working properly (as assessed using the tabs command in Stata) and/or there are apparent issues with the data collection (e.g., erroneous skip patterns), we will address all identified issues then resume data collection until the final sample is achieved.

We will descriptively report unadjusted values for primary and secondary outcomes. We will use a two-sided critical alpha of 0.05 to conduct all statistical tests. Per CONSORT guidelines, we will not test for balance in covariates. Primary analyses will be intent-to-treat, including all eligible participants with non-missing data for the outcome being analyzed.

For all primary, secondary, and other outcomes, we will assess whether the outcomes vary by study arm. For the primary outcomes, we will use two-sample t-tests for means. If there are imbalances in potentially

confounding factors between arms, we will use linear regressions. For the secondary and other outcomes, we will use linear regression.

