## **Sensitivity Analyses**

We will describe dropout (defined as entering the store but not completing the purchasing task) by study arm. Dropout is defined as passing the screener survey but not completing the exit survey (i.e., dropping out during the shopping task or during the exit survey). If differential dropout is identified, we will consider sensitivity analyses to handle missing outcome data, such as inverse probability weighting. We will compare the main effects to the primary results if the number of participants excluded from a moderation analysis because of missing demographic data warrants it.

For all analyses, all pairwise comparisons of means will be examined for all outcomes. We will consider a result statistically significant at  $p < 0.05$ .

In exploratory analyses, we will examine whether any of the collected participant characteristics (see list below) moderate the intervention effects on the primary outcomes:

- a. Age
- b. Gender
- c. Region
- d. Education
- e. Race
- f. Household monthly income
- g. Household size
- h. Parent/caregiver
- i. Marital status
- j. Experience with online shopping for clothes, electronics, furniture, or home appliances
- k. Experience with online grocery shopping
- l. Hunger levels at time of survey
- m. BMI
- n. Self-reported health status
- o. Diabetes
- p. Heart disease

To test whether these characteristics moderate the effect of each intervention on nutrient content, we will fit a series of regression models (one for each potential moderator), with trial arm, the moderator (specified as dummy variables), and their interaction as predictors. We will use a Wald chunk test to determine the joint significance of the interaction terms. We will quantitatively evaluate the presence of moderation by calculating the marginal effect of each intervention on the outcome at different levels of the moderating variable. If the pattern of main results is similar between intervention arms (magnifying glass label based on ANVISA nutrient profile model, magnifying glass label based on PAHO nutrient profile model), we will consider combining intervention arms for the moderation analysis.

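### Does scoring the identification outcome against the PAHO model, which is also one arm's label, bias the comparison of labels?

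*SAP*

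**What the plan says.** The Hypotheses section of the SAP gives the purpose as to "assess the impact of different nutrient profiles for magnifying glass front-of-package labels on consumer choices". Sensitivity Analyses names the two intervention arms: "magnifying glass label based on ANVISA nutrient profile model, magnifying glass label based on PAHO nutrient profile model". The third arm has no label.

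Secondary Outcomes lists six outcomes. One is the ability to recognise high nutrient content in unhealthy products, judged "as per the PAHO nutrient profile model, which is stricter than" the ANVISA model. The fifth secondary hypothesis predicts, for each label arm against the no-label control, "Higher ability to identify high sugar/saturated fat/sodium content of unhealthy products".

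On analysis, Statistical Methods says: "For the secondary and other outcomes, we will use linear regression". It sets a two-sided alpha of 0.05. Sensitivity Analyses adds that "all pairwise comparisons of means will be examined for all outcomes", which brings in ANVISA against PAHO on this outcome too.

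**The concern.** The key that decides a right answer is the same model that generates one arm's label. By the SAP's own account that model is the stricter one, so some nutrients may be high under PAHO yet carry no ANVISA flag. On such an item the PAHO participant sees the keyed answer. The ANVISA participant sees nothing, may sensibly conclude that the nutrient is not high, and is scored wrong.

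The score would then combine how well people use a label with how many products each model covers. If the outcome were meant to measure label comprehension, PAHO would have a built-in advantage. A real ANVISA gain on flagged items could also be offset by losses on unflagged ones, and a working label could look inert against control.

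**Working it through.** The SAP states no figure for this outcome, so there is nothing to reproduce. The check has two parts: what the comparison estimates, and how large the gap could be.

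**What is estimated**

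1. *Treatment.* Both intervention arms use a magnifying-glass label and differ in the nutrient profile model behind it. Hypotheses and Statistical Methods both present the model as the thing whose effect is sought. Coverage, meaning which nutrients get a flag, is therefore the treatment contrast and not a confounder.
2. *Outcome.* Every participant in every arm is scored against one key. A no-label arm has no label of its own to be scored against, so a comparison with control needs a common standard. Scoring each label arm by its own label would make the outcome a different variable in each arm.
3. *Estimate.* With random assignment and a common key, the difference in mean score is unbiased for the effect of being shown one label rather than another on recognising PAHO-high content. If a missing ANVISA flag lowers recognition, that is an effect of the looser threshold, and the outcome detects it.

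**How large the gap could be (all response rates assumed)**

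Let 60% of participants answer as the label indicates and the rest answer high half the time. Let control answer high 50% of the time. Let f be the share of PAHO-high items that ANVISA does not flag, and m the probability of answering high when no flag is shown in the ANVISA arm.

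- Flag shown: 0.6 × 1 + 0.4 × 0.5 = 0.80. This is the PAHO score.
- ANVISA score: (1 − f) × 0.80 + f × m.
- Gap, PAHO minus ANVISA: f × (0.80 − m).

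If a missing flag is read as strongly as a present one, m = 0.6 × 0 + 0.4 × 0.5 = 0.20. If it leaves people where control is, m = 0.50.

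| f | ANVISA, m = 0.20 | Gap | ANVISA, m = 0.50 | Gap |
|---|---|---|---|---|
| 0 | 80% | 0 | 80% | 0 |
| 0.2 | 68% | 12 points | 74% | 6 points |
| 0.5 | 50% | 30 points | 65% | 15 points |

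ANVISA falls to the control rate of 50% only with both f = 0.5 and m = 0.20. With m = 0.50 it is still 15 points above control at f = 0.5. The SAP gives neither f nor m. The item set belongs in the protocol or questionnaire, which is not shown.

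**Chance of a significant ANVISA-PAHO difference**

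A second illustration takes equal reading accuracy c in both label arms, a share q of judgements on which the models disagree, and 3,000 × 0.94 / 3 = 940 per arm. The 6% loss is from Sample Size and Power; equal allocation is assumed. The gap is c − [(1 − q)c + q(1 − c)] = q(2c − 1).

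- c = 0.8, q = 0.05: 3 points, 35% chance of p < 0.05.
- c = 0.8, q = 0.10: 6 points, 87%.
- c = 0.8, q = 0.20: 12 points, above 99%.
- c = 0.6, q = 0.10: 2 points, 14%.

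These are not false-positive rates. The null hypothesis is equal mean recognition of PAHO-high content. Whenever q > 0 and c > 0.5 that null is false, so the percentages are power to detect a true difference.

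**Would splitting the items be better?**

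On items flagged by both models, both arms see the same flag and the expected scores are 0.80 − 0.80 = 0 apart. The whole gap, f × (0.80 − m), comes from items flagged by PAHO alone. Basing the ANVISA-PAHO contrast on the shared items would remove nearly everything the trial varies and give a result close to null by design.

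**The case for a change.** The strongest case for the concern is that the SAP does not spell out that it means recognition of PAHO-defined content as opposed to skill in using the label. It still tests ANVISA against PAHO at p < 0.05 on a PAHO-keyed score, with no breakdown by item type. A reader of the results could take a PAHO advantage to mean that the PAHO label is better understood. Even a modest share of discordant items could make that difference significant.

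The arithmetic stands, and so does the warning about interpretation: a difference between the label arms on this score should not be described as a difference in comprehension. A separate summary of PAHO-only items could be informative. But the SAP makes no comprehension claim. It names the key and states in the same sentence that it is the stricter model, which points to a deliberate choice. The ANVISA-PAHO contrast on this outcome arises only from the general sentence on pairwise comparisons and not from a stated hypothesis.

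The parenthesis might instead be read as defining which products count as unhealthy. PAHO would then select the products and no other standard for high content would be stated, so this reading does not create a bias either.

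**Conclusion.** The concern does not hold. The outcome has one stated standard for all arms, the arms differ in the factor the trial sets out to study, and randomisation makes the comparison valid for the outcome as defined. The fifth secondary hypothesis can be tested as written. If ANVISA gains less over control than PAHO does, that is a finding about the looser model and not a scoring artefact.

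The size is unknown from the document. Under the assumed rates the gap is anywhere from 0 to 30 points for f between 0 and 0.5, and the large values need both many PAHO-only items and readers who treat a missing flag as strongly as a present one. One of six secondary outcomes is involved, in a study that calls itself exploratory, and the primary outcomes are untouched. What remains is care in wording the results and an optional extra breakdown. Neither corrects a wrong rule or figure in the plan.

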## **STATISTICAL CONSIDERATION**

### **Statistical Methods**

The study is a randomized controlled trial. The analysis will rely on random assignment to identify the effect of each type of front-of-package label nutrient profile model on consumer choices.

We will conduct a soft launch with 100 participants to check randomization and data quality. If randomization is working properly and there are not apparent issues with the data collection, we will resume data collection until the final sample is achieved. The original participants from the soft launch will be included in the final dataset. If randomization is not working properly (as assessed using the tabs command in Stata) and/or there are apparent issues with the data collection (e.g., erroneous skip patterns), we will address all identified issues then resume data collection until the final sample is achieved.

We will descriptively report unadjusted values for primary and secondary outcomes. We will use a two-sided critical alpha of 0.05 to conduct all statistical tests. Per CONSORT guidelines, we will not test for balance in covariates. Primary analyses will be intent-to-treat, including all eligible participants with non-missing data for the outcome being analyzed.

For all primary, secondary, and other outcomes, we will assess whether the outcomes vary by study arm. For the primary outcomes, we will use two-sample t-tests for means. If there are imbalances in potentially

confounding factors between arms, we will use linear regressions. For the secondary and other outcomes, we will use linear regression.

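### The default primary t-tests forgo whatever precision the collected participant characteristics could offer; a prespecified adjusted regression would recover it at almost no cost

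*SAP*

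**What the plan says.** The SAP's Statistical Methods section sets the default for the three primary nutrients: "For the primary outcomes, we will use two-sample t-tests for means". A sentence that opens "If there are imbalances in potentially" confounding factors then brings in linear regression for these outcomes. It names no covariates and gives no threshold. The same section says "Per CONSORT guidelines, we will not test for balance in covariates".

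For the remaining outcomes the method is already regression: "For the secondary and other outcomes, we will use linear regression". Covariates are again unstated.

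The Sensitivity Analyses section lists 16 collected characteristics (items a to p), among them "Household size", age, gender, region, education, income and parent/caregiver status. Their stated use is exploratory: "whether any of the collected participant characteristics (see list below) moderate the intervention effects on the primary outcomes".

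Sample Size and Power caps the trial at 3,000 participants and allows for a 6% loss from removing extreme values. It states at least 90% power for ANVISA versus control on saturated fat and on sugar, and for PAHO versus control on saturated fat. It makes no power statement for sodium under either label, or for PAHO on sugar.

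**The concern.** In a randomized trial, the main reason to adjust for a covariate is that it predicts the outcome, not that the arms happen to differ on it. The SAP ties adjustment of the primary outcomes to the second reason alone. If the arms are balanced, the t-test stands, and any variation in basket nutrients explained by household size, age, income and so on stays in its error term. Defining the imbalance trigger more tightly would not recover that precision.

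What is at stake is the width of the confidence intervals and the power for the six primary contrasts (two labels by three nutrients), most of all the three with no stated power. The SAP treats the sample size as fixed at its maximum, so efficiency of analysis is the remaining way to gain precision. In a linear model the adjusted arm difference targets the same mean difference, so interpretation does not change.

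**Working it through.** **Inputs from the SAP**
- Total sample size 3,000 and loss 6% (Sample Size and Power): 3,000 × 0.94 = 2,820 analysed.
- Two-sided alpha 0.05 (Statistical Methods): critical value 1.96.
- 16 collected characteristics (Sensitivity Analyses).

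**Assumptions, because the SAP gives no figure**
- R-squared, the share of within-arm outcome variance that the covariates explain: 2%, 5%, 10%, 15%.
- Starting power of 80% or 60% for a contrast. These are illustrations only.
- Equal allocation to three arms, 2,820 / 3 = 940 per arm, needed only for the standardized difference in step 1.

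**Step 1. The SAP's own figure.** The stated 90% power cannot be reproduced, since no mean difference, standard deviation or allocation ratio is given. With 940 per arm, 90% power corresponds to a standardized difference of (1.96 + 1.2816) × √(2/940) = 0.1495.

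**Step 2. Gain in effective sample size.** Adjustment multiplies the residual standard deviation, and so the standard error, by √(1 − R²). The equivalent sample size is 2,820 / (1 − R²).

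**Step 3. Gain in power.** New power = Φ[(1.96 + z) / √(1 − R²) − 1.96], where z is the normal quantile of the starting power (0.8416 for 80%, 0.2533 for 60%).

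| Assumed R² | Standard error falls by | Equivalent sample size | Extra participants | 80% becomes | 60% becomes |
|---|---|---|---|---|---|
| 2% | 1.0% | 2,878 | 58 | 80.8% | 60.9% |
| 5% | 2.5% | 2,968 | 148 | 82.0% | 62.2% |
| 10% | 5.1% | 3,133 | 313 | 84.0% | 64.5% |
| 15% | 7.8% | 3,318 | 498 | 86.0% | 67.0% |

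Worked line for R² = 10%: 2,820 / 0.90 = 3,133, a gain of 313. For power, (1.96 + 0.8416) / √0.90 = 2.953; 2.953 − 1.96 = 0.993; Φ(0.993) = 0.840.

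**Step 4. Cost in degrees of freedom.** With p covariate terms, the approximate R-squared at which adjustment breaks even is p / (2,820 − 3). For p = 1 this is 1/2,817 = 0.0004. For p = 16 it is 16/2,817 = 0.006. For an assumed 45 dummy terms it is 45/2,817 = 0.016. A short list therefore loses almost nothing even if it predicts poorly.

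**The case against.** The strongest reply is that nothing here is invalid. The SAP relies on random assignment, under which the unadjusted t-test is unbiased for the mean difference, and the power statement was made for t-tests, so analysis and sizing agree. That stands: the point is about efficiency, not error.

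It is also fair that prognostic strength is assumed. The SAP reports no correlation, R-squared or standard deviation. Its Outliers and Exclusions section shows that participants shop from a list, which may loosen the link between household size and basket totals. The gain could be close to zero, and at an R-squared of 2% to 5% it is small. This is why the result is given as a range.

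A reader might infer several stronger things that the SAP does not support:
- That every label effect is affected. The unadjusted default covers only the three primary nutrients; secondary and other outcomes go to linear regression, with covariates unstated.
- That the characteristics serve only as moderators. The imbalance clause may bring some of them into the primary regression, although it names none.
- That the sodium contrasts and PAHO on sugar are underpowered and adjustment would rescue them. The SAP gives no power for them, and if the true effect is near zero no covariate helps.
- That any listed characteristic is safe to adjust for. The SAP does not say when each is asked, and it mentions both a screener and an exit survey. An item asked after shopping could respond to the label, or be missing because of it.

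The last point limits the choice of covariates and the handling of missing values. It does not remove the case for adjustment.

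**Conclusion.** The point holds as a forgone gain in precision for the primary outcomes. The default test is valid, and its results would not be wrong. On assumed R-squared values of 2% to 15%, the forgone gain is equivalent to about 58 to 498 participants on top of 2,820, or about 1 to 6 percentage points on an assumed 80% power. The true figure depends on how well the characteristics predict basket nutrients, which the SAP does not show. The change is still worth making: the break-even R-squared is about 0.006 for 16 terms, the estimand is unchanged, the data are already collected, and half of the primary label-versus-control contrasts have no stated power.

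**What to change.** - For each primary nutrient, prespecify one linear regression on arm plus a short fixed list of characteristics that are asked before the shopping task or that the label cannot alter. Examples are age, gender, region, education, income, household size and parent/caregiver status. Fit it whatever the observed balance, with heteroscedasticity-robust standard errors.
- State in the SAP when each covariate is asked. Leave out hunger and self-rated health unless they are asked before shopping.
- Keep participants with missing covariates in the analysis by simple imputation that ignores arm. Use a 'not reported' level only for items asked before exposure, where missingness cannot depend on arm.
- Report the unadjusted t-test as a sensitivity analysis, and drop the switch that depends on observed imbalance. This also removes the conflict between a trigger with no threshold and the decision not to test balance.

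The cost is a change of SAP wording and one regression per nutrient, with no new data and no more participants. The downside is a negligible loss of degrees of freedom, and possibly little gain if the covariates predict weakly.

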## **Sample Size and Power**

This is an exploratory study and the sample size was maximized at 3,000 participants. Data from a pilot study of 300 participants conducted in December 2022 and January 2023 showed that, accounting for a loss of 6% of participants after excluding the top 2% of values for total saturated fat, sodium and sugar, 3,000 participants would provide at least 90% power to 0.05-level two-sided t-tests for mean differences between ANVISA and the control in total saturated fat and sugar, between PAHO and the control in total saturated fat, and between each arm in the proportion of ultra-processed products checked out (equal and unequal variances).

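### The SAP prescribes linear regression for all secondary outcomes without naming a standard error; under the usual equal-variance default, tests on label noticing can miss the stated 0.05 level in either direction

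*SAP*

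**What the plan says.** Statistical Methods in the SAP assigns one model to every outcome below the primary ones: "For the secondary and other outcomes, we will use linear regression". It does not say how the standard errors are computed, or whether one model holds all three arms or a separate model is fitted to each pair. The level is fixed in the same section: "We will use a two-sided critical alpha of 0.05 to conduct all statistical tests".

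Secondary Outcomes ends its list with "and noticing of the product label" and predicts, relative to a control without labels, "Higher noticing of the front-of-package label". The response scale is not given. Sensitivity Analyses adds that "all pairwise comparisons of means will be examined for all outcomes", so ANVISA is compared with PAHO on noticing as well.

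Unequal variances appear only under Sample Size and Power, which claims power "between each arm in the proportion of ultra-processed products checked out (equal and unequal variances". The analysis text has no counterpart.

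**The concern.** Unqualified linear regression is ordinarily read as least squares with one residual variance shared by all arms. Each pairwise contrast then borrows variance from the third arm. That is harmless when the three variances agree.

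Noticing is the outcome where they are least likely to agree. If it is recorded as yes/no, its variance is p(1−p), so the difference in rates that the SAP predicts between control and label arms will generally make the variances differ too. The ANVISA–PAHO comparison then uses a standard error partly set by the control arm, which is not in the comparison. A larger sample does not cure this, because the ratio of true to model standard error does not depend on n.

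At stake are the p-values and interval widths for such outcomes, and the fact that two analysts could both follow the SAP and report different ones. The estimated differences in means or proportions are not at stake.

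**Working it through.** **The plan's own figure.** The SAP states at least 90% power with 3,000 participants for certain nutrient totals and the ultra-processed proportion. It cannot be reproduced, because no effect sizes or standard deviations are given. Inverting it with 1,000 per arm gives (1.960 + 1.282) × √(2/1000) = 0.145 SD; with 940 per arm (6% lost) it gives 0.150 SD. The SAP states no power or error rate for noticing.

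**Inputs from the SAP.** Two-sided 0.05, all pairs compared, 3,000 participants in total. The 6% loss concerns outlying nutrient totals and does not enter the calculation below.

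**Assumptions, not in the SAP.** Yes/no noticing; 1:1:1 allocation (1,000 per arm); one three-arm model with the classical standard error; control rate c between 0 and 50%; a common label-arm rate p between 20 and 90%.

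**Formulas.** Let v_c = c(1−c), v = p(1−p), and pooled variance V = (v_c + 2v)/3.

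- ANVISA versus PAHO: true SE / model SE = √(v/V). Type I error = 2 × [1 − Φ(1.96 / ratio)].
- Label versus control: ratio = √((v_c + v)/(2V)). Coverage = 2Φ(1.96 / ratio) − 1.

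**Control 10%, labels 50%.** v_c = 0.09, v = 0.25, V = 0.59/3 = 0.1967.

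- ANVISA–PAHO: ratio = √(0.25/0.1967) = 1.127; 1.96/1.127 = 1.74; type I error 8.2%.
- Label–control: ratio = √(0.34/0.3933) = 0.930; coverage 96.5%.

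**Control 30%, labels 90%.** v_c = 0.21, v = 0.09, V = 0.39/3 = 0.13.

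- ANVISA–PAHO: ratio = √(0.09/0.13) = 0.832; type I error 1.8%.
- Label–control: ratio = √(0.30/0.26) = 1.074; coverage 93.2%.

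**Type I error (%) for ANVISA versus PAHO over the range.**

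| Control rate | Labels 30% | Labels 50% | Labels 80% | Labels 90% |
|---|---|---|---|---|
| 0% | 11.0 | 11.0 | 11.0 | 11.0 |
| 5% | 9.1 | 9.4 | 8.6 | 7.2 |
| 10% | 7.8 | 8.2 | 7.0 | 5.0 |
| 20% | 6.0 | 6.6 | 5.0 | 2.8 |
| 30% | 5.0 | 5.7 | 3.9 | 1.8 |
| 50% | 4.3 | 5.0 | 3.3 | 1.3 |

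**Simulation check.** With 200,000 simulated trials at 1,000 per arm and rates of 10/50/50%, the pooled three-arm test rejected in 8.3%, a robust (HC1) test in 5.1%, and a regression on the two label arms alone in 5.1%. At 30/90/90% the pooled test rejected in 1.8% and the robust test in 4.9%. HC1 and HC3 hardly differ here: with arm-only predictors they scale the variance by 3000/2997 = 1.001 and (1000/999)² = 1.002.

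**Continuous outcome.** With r the control/label SD ratio, type I error = 2 × [1 − Φ(1.96 × √((r² + 2)/3))]. This gives 5.8% at r = 0.9 and 4.3% at r = 1.1.

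**The case against.** The strongest reply is that the SAP does not commit to a pooled variance. Regression with robust errors satisfies its wording, and so do separate two-arm regressions; both hold the level at about 5%. This stands. The defect is silence on the standard error, not the choice of a wrong one. Silence still matters, because the default is the version that can fail.

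The 8% figure also needs a yes/no scale, particular rates and equal arms, none of them in the SAP. The questionnaire may settle the scale elsewhere. This stands too, which is why the result is given as a range.

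A reader might go further and infer that ANVISA–PAHO intervals are always too narrow and label–control intervals always too wide. The figures do not support that: the pattern reverses at 30/90% and disappears at 10/90%, where all three variances are equal. Nor may the 96.5% coverage be turned into a test level for label versus control, since at 10% against 50% the null is false.

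Finally, every numbered hypothesis compares a label with control, and the study calls itself exploratory. That limits the weight of the point. But the Hypotheses section gives the purpose as comparing nutrient profiles, and Sensitivity Analyses commits to testing every pair.

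**Conclusion.** The point holds as a gap in specification with a nearly free remedy. Under the ordinary default, and if noticing is yes/no with equal arms, the ANVISA–PAHO type I error is about 8% at 10/50%, and between about 1% and 11% over the rates examined. Label–control coverage can fall on either side of 95%.

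It would be tempting to say that all secondary outcomes carry wrong error bars. The SAP does not support this. Only noticing has a clear reason for markedly unequal variances. For the percentage of ultra-processed products and the perception outcomes no arm difference in variance has been shown, and a 10% difference in SD moves the error only to 4.3% or 5.8%. Effect estimates are unaffected throughout.

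The planned primary t-tests are not exposed in the same way, since each uses only the two arms it compares.

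**What to change.** In Statistical Methods, specify linear regression with heteroscedasticity-robust (e.g. HC3) standard errors for the secondary and other outcomes. With arm-only predictors the coefficients do not change and remain differences in means or proportions. The ANVISA–PAHO test then runs at about 0.05 whichever way the variances differ.

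The cost is one phrase in the SAP and one software option (in Stata, vce(hc3)). At about 1,000 per arm the loss of efficiency is negligible, and no new data or change of sample size is needed.

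Naming the unequal-variance t-test for the primary outcomes would do no harm but changes little: with equal arms its statistic equals the pooled one, and only the degrees of freedom differ.
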